7.1. Overview of Planned Adverse Events Analyses

Table 3 provides an overview of the planned adverse events analyses with full details of data displays being presented in Appendix 9: List of Data Displays.

Table 3 Overview of Planned Adverse Event Analyses

Display Type	Absolute		
	Summary		Individual
	T	F	L
Adverse Events (AEs)			
All AEs by SOC and PT	Y		Y
All AEs by Maximum Intensity	Y		
Drug-Related AEs by SOC and PT	Y		
Drug-Related AEs by Maximum Intensity	Y		
Subject Numbers for Individual AEs			Y
Relationship Between AE SOCs, PT and Verbatim Text			Y
Serious and Other Significant AEs			
Serious AEs			Y
AEs Leading to Withdrawal from Study			Y

NOTES:

- T = Table, F = Figures, L = Listings, Y = Yes display generated, SOC = System Organ Class, PT = Preferred Term.
- Summary = Represents TF related to any summaries (i.e. descriptive statistics) of the observed raw data.
- Individual = Represents FL related to any displays of individual subject observed raw data.

7.2. Overview of Planned Clinical Laboratory Analyses

Table 4 provides an overview of the planned analyses, with further details of data displays being presented in Appendix 9: List of Data Displays.

Table 4 Overview of Planned Clinical Laboratory Analyses

Display Type	Absolute			Change from BL		
	Summary		Individual	Summary		Individual
	T	F	L	T	F	L
Chemistry						
Chemistry Data	Y		Y	Y		Y
Chemistry Results Relative to Normal Range				Y		
All Chemistry Data for Subjects with any Value of Potential Clinical Concern/PCI			Y			Y
Hematology						
Hematology Data	Y		Y	Y		Y
Hematology Results Relative to Normal Range				Y		
All Hematology Data for Subjects with any Value of Potential Clinical Concern/PCI			Y			Y
Urinalysis						
Dipstick Data (Glucose, Protein, Blood, Ketones, Bilirubin, Urobilinogen)	Y		Y*			
Gravity and pH	Y		Y			
Hepatobiliary (Liver)						
Liver Monitoring/Stopping Event Reporting			Y			
Medical Conditions for Subjects with Liver Stopping Events			Y			
Substance Use for Subjects with Liver Stopping Events			Y			

NOTES:

- T = Table, F = Figures, L = Listings, Y = Yes display generated, PCI = Potential Clinical Importance
- Summary = Represents TFL related to any summaries (i.e. descriptive statistics) of the observed raw data.
- Individual = Represents FL related to any displays of individual subject observed raw data.

*: If blood or protein is abnormal, microscopic examination will be included.

7.3. Overview of Planned Other Safety Analyses

Table 5 provides an overview of the planned analyses, with further details of data displays being presented in Appendix 9: List of Data Displays.

Table 5 Overview of Planned Other Safety Analyses

Display Type	Absolute			Change from BL		
	Summary		Individual	Summary		Individual
	T	F	L	T	F	L
ECG						
ECG Findings	Y		Y			
ECG Values	Y		Y	Y		Y
All ECG Values for Subjects with any Value of PCI			Y			
Vital Signs						
Vitals Values	Y		Y	Y		Y
All Vital Signs for Subjects with any Value of PCI			Y			
Ophthalmic examinations						
Ophthalmic examinations			Y			

NOTES:

- T = Table, F = Figures, L = Listings, Y = Yes display generated, PCI = Potential Clinical Importance
- Summary = Represents TFL related to any summaries (i.e. descriptive statistics) of the observed raw data.
- Individual = Represents FL related to any displays of individual subject observed raw data.

8. PHARMACOKINETIC ANALYSES

8.1. Overview of Planned Pharmacokinetic Analyses

The pharmacokinetic (PK) analyses will be based on the Pharmacokinetic population, unless otherwise specified. These analyses will be performed in each part.

Table 6 provides an overview of the planned analyses, with full details being presented in Appendix 9: List of Data Displays.

Table 6 Overview of Planned Pharmacokinetic Analyses

Display Type	Untransformed				Log-Transformed				
	Summary		Individual		Stats analysis	Summary		Individual	
	F	T	F	L		F	T	F	L
Descriptive statistics									
Blood Drug Concentrations	Y [1] [2]	Y	Y [1]	Y					
Derived PK Parameters	Y	Y		Y			Y		
Statistical Analysis of PK Parameters									
Power model (Part 1)					Y				
Food effect (Part 2)					Y				

NOTES:

- T = Table, F = Figures, L = Listings, Y = Yes display generated.
- Summary = Represents TFL related to any summaries (descriptive statistics) of the observed raw data.
- Individual = Represents FL related to any displays of individual subject observed raw data.
- 1. Linear and Semi-Log plots will be created on the same display.
- 2. Separate Mean (+ SD) and Median plots will be generated.

8.2. Drug Concentration Measures

Blood concentrations of GSK1325756 will be listed and summarised by part, treatment and nominal time. Standard summary statistics will be calculated (i.e. mean, standard deviation, median, minimum and maximum).

Individual blood concentration-time profiles and median/mean profiles by treatment will be plotted. Each of the figures will contain one plot on the untransformed scale (i.e. a linear plot) and one plot on the log transformed scale (i.e. log-linear plot).

Refer to Appendix 4: Data Display Standards & Handling Conventions (Section 10.4.4 Reporting Process & Standards).

8.3. Pharmacokinetic Parameters

8.3.1. Deriving Pharmacokinetic Parameters

- Derivation of pharmacokinetic parameters will be performed by, or under the direct auspices of, Clinical Pharmacology & Science Promotion Office, GlaxoSmithKline K.K.
- Refer to Appendix 4: Data Display Standards & Handling Conventions (Section 10.4.4 Reporting Process & Standards).
- The pharmacokinetic parameters will be calculated by standard non-compartmental analysis using WinNonlin (version 6.3 or higher)
- All calculations of non-compartmental parameters will be based on actual sampling times recorded during the study.
- Pharmacokinetic parameters described in Table 7 will be determined from blood GSK1325756 concentration-time data, as data permits.

Table 7 Derived Pharmacokinetic Parameters

Parameter	Parameter Description
AUC(0-24) (h*ng/mL)	
Area under the concentration-time curve will be calculated to fixed nominal time 24 hours after administration (AUC(0-24)), using the combination of linear and logarithmic trapezoidal methods (i.e., Linear Up/Log Down calculation method in Phoenix WinNonlin Professional).
 
If a sampling time deviation occurred at nominal time 24 hours after administration (and 24 < t), AUC(0-24) will be calculated using the concentration at time 24 hours after administration post-dose estimated by the method of interpolation.
 
If nominal time 24 hours after administration > t (or if the concentration at time 24 hours after administration was below then limit of quantification), then the concentration (y) at time 24 hours after administration is estimated using lambda_z and last observed Ct according to the formula:
 $y = Ct(\text{obser}) \times e^{-\lambda_z(24-t)}$ 
Then the following equation will be used to calculate (AUC(0-24)) where t is the time of last quantifiable blood concentration.
 $\text{AUC}(0-24) = \text{AUC}(0-t) + \text{AUC}(t-24)$ 
If lambda_z is not estimable, a partial AUC is not calculated (when 24 > t).

AUC(0-t) (h*ng/mL)	Area under the concentration-time curve from zero time (pre-dose) to the time of the last quantifiable concentration (AUC(0-t)) will be calculated by a combination of linear and logarithmic trapezoidal methods. The linear trapezoidal method will be employed for all incremental trapezoids arising from increasing concentrations and the logarithmic trapezoidal method will be used for those arising from decreasing concentrations (i.e., Linear Up/Log Down calculation method in Phoenix WinNonlin Professional).
AUC(0-inf) (h*ng/mL)	Area under the concentration-time curve from zero time (pre-dose) extrapolated to infinite time (AUC(0-inf)) will be calculated as follows: $\text{AUC}(0-\text{inf}) = \text{AUC}(0-t) + Ct / \lambda_z$
Cmax (ng/mL)	Maximum observed concentration will be obtained directly from the concentration-time data.
Tmax (h)	Time to first occurrence of Cmax will be obtained directly from the concentration-time data.
t1/2 (h)	Terminal phase half-life will be calculated as follows: $t_{1/2} = \ln 2 / \lambda_z$
tlag (h)	Lag time before observation of drug concentrations in sampled matrix.

Parameter	Parameter Description
tlast (h)	The time of the last measurable (positive) concentration.
%AUCex (%)	The area under the curve (AUC) from the last predicted non-zero concentration value to infinity as a percentage of the area under the curve extrapolated to infinity.
lambda_z (/h)	The first order rate constant associated with the terminal (log-linear) portion of the curve.
lambda_z_lower (h)	The lower limit on time for values to be included in the calculation of Lambda z.
lambda_z_upper (h)	The upper limit on time for values to be included in the calculation of Lambda z.
#pts	The number of time points used in computing Lambda z.
R2	The goodness of fit statistic for the terminal elimination phase.

NOTES:

- Additional parameters may be included as required.
- Lambda_z is the terminal phase rate constant.
- Ct is the last observed quantifiable concentration.

8.3.2. Summary of Pharmacokinetic Parameters

- For each of these parameters, except for tmax, tlag and tlast, the following summary statistics will be calculated for each treatment:
 - Non-transformed: arithmetic mean, median, maximum, minimum, 95% confidence interval for the arithmetic mean and standard deviation
 - Loge-transformed: geometric mean, 95% confidence interval for the geometric mean, standard deviation of logarithmically transformed data and between geometric coefficient of variation (CVb (%))
- Median, maximum, minimum, arithmetic mean, 95% confidence interval and standard deviation will be calculated for tmax, tlag and tlast.

8.3.3. Statistical Analysis of Pharmacokinetic Parameters

8.3.3.1. Dose proportionality

For Part 1, the PK-dose relationship will be investigated graphically in order to assess dose proportionality of GSK1325756. Plots of AUC (0-t) and Cmax versus dose will be plotted.

Also statistical analyses will be carried out to explore the dose proportionality of GSK1325756 as assessed by AUC(0-t) and Cmax, using the Power Model:

$$\log_e (Y_{ij}) = \mu + S_i + \beta * \log_e (D_j) + \varepsilon_{ij}$$

Y_{ij} : PK parameter (AUC(0-t), Cmax) on the j th dose for i th subject

μ : Overall mean (Intercept)

S_i : Random effect for subject i following normal distribution $N(0, \sigma_b^2)$

β : Slope for \log_e transformed dose

D_j : Dose ($j=1:10\text{mg}$, $2:50\text{mg}$, $3:100\text{mg}$)

ε_{ij} : Random error following normal distribution $N(0, \sigma_w^2)$

Following loge-transformation, AUC (0-t) and Cmax will be separately analyzed, if data permitted. A mixed effect model will be fitted with the loge transformed dose and period as fixed effects. Subject will be fitted as a random effect. The Kenward & Roger (KR) degrees of freedom approach will be used. Point estimates and their associated 90% confidence intervals will be constructed.

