5.2. Number of Participants

Part 1 and Part 2

Sufficient participants will be randomised such that approximately 18 and 16 evaluable participants complete the study of each part. If subjects prematurely discontinue the study, additional subjects may be enrolled as replacement subjects and assigned to the same treatment sequence, if applicable, at the discretion of the sponsor in consultation with the investigator.

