10.3.2. Pharmacokinetic Analyses

All PK analyses will be performed on the PK Population.

Statistical Analysis Methods

Blood GSK1325756 concentration-time data will be analysed by non-compartmental methods with WinNonlin. Calculations will be based on the actual sampling times recorded during the study.

From the blood concentration-time data, the following PK parameters will be determined, as data permit: AUC(0-t), AUC(0-24), AUC(0-inf), Cmax, tmax, apparent t1/2, Tlag and tlast.

PK data will be presented in graphical and/or tabular form and will be summarised descriptively.

Listings will be generated and summary statistics (n, arithmetic mean with associated 95% CI, standard deviation, minimum, median, maximum, geometric mean with associated 95% CI, SD on log-scale and %CVb or %CVw) will be calculated for each derived blood PK parameter for each group dose in each Part.

Part 1:

The PK-dose relationship will be examined graphically by plotting derived blood PK parameters (AUC(0-t) and Cmax) for each group dose.

Dose proportionality for PK parameters (AUC(0-t) and Cmax) will be assessed by using a power model as described below:

$$\log(\text{PK parameter}) = \beta_0 + \beta_1 \cdot \log(\text{dose})$$

where β_0 is the intercept and β_1 is the slope.

Following loge-transformation, AUC(0-t) and Cmax will be separately analyzed using a power model with fixed effect terms for log-dose, as data permitted. Subjects will be assessed in model as random effect, and degree of freedom will use Kenward-Roger. Point estimates for the slopes of PK parameters and their associated 90% CIs will be constructed.

Part 2:

An estimation approach will be used to assess the food effect of GSK1325756 on primary PK parameters, where point estimates and corresponding 90% CIs will be constructed to provide a plausible range of values for the true comparisons of interest.

To estimate the food effect on the primary PK endpoints, data from Period 1 and Period 2 will be used. Following loge-transformation, AUC(0-t) and Cmax of GSK1325756 will be separately analysed using a mixed effects model with fixed effect terms for regimen (the treatment variable can be applied as this contains whether the subject is on fed or fasted for that particular period) and period. Subject will be treated as a random effect in the model.

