2. SUMMARY OF KEY PROTOCOL INFORMATION

2.1. Changes to the Protocol Defined Statistical Analysis Plan

There were no changes or deviations to the originally planned statistical analysis specified in the protocol [Dated: 11/APR/2017].

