8.3.3.2. Food effect

For Part 2, statistical analyses will be carried out to assess treatment (food effect) of GSK1325756 for AUC(0-t) and Cmax using Mixed effect model:

$$\log_e (Y_{ij}) = \mu + S_i + t_j + p_k + \varepsilon_{ij}$$

Y_{ij} : PK parameter (AUC(0-t), Cmax) on the j th treatment for i th subject

μ : Overall mean (Intercept)

S_i : Random effect for subject i following normal distribution $N(0, \sigma_b^2)$

t_i : Treatment effect ($j=\text{fasted, fed}$)

p_k : Period effect ($k=\text{period 1, period 2}$)

ε_{ij} : Random error following normal distribution $N(0, \sigma_w^2)$

Following loge-transformation, AUC (0-t) and Cmax will be separately analysed using a mixed effects model fitting terms for treatment and period as fixed effects, and subject as a random effect in order to assess food effect of GSK1325756 (Fed vs. Fasted). The Kenward & Roger (KR) degrees of freedom approach will be used.

Point estimates for the adjusted means on the loge scale, the mean difference between treatments and associated 90% confidence interval will be constructed using the residual variance. The point estimate and confidence interval will then be exponentially back-transformed to obtain adjusted (least square) geometric means for each treatment, and point estimates and associated 90% confidence interval for the ratio of fasted/fed.

Estimates of within-subject variability (CVw (%)) for AUC (0-t) and Cmax will also be provided. CVw (%) will be calculated based on the loge-normal distribution where:

CVw (%)= SQRT(exp(MSE)-1) * 100. (MSE is the residual mean squared error from the model)

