10.4.2. Sequence group Display Descriptors

Sequence Group Descriptions			
RandAll NG		Data Displays for Reporting	
Code	Description	Description [1]	Order
A	X1/X2/P	A	1
B	X1/P/X3	B	2
C	P/X2/X3	C	3
D	X2/X4	D	4
E	X4/X2	E	5

NOTES:

1. Footnote will be added in displays as follows.
A: 10mg (Fed) / 50mg (Fed) / Placebo (Fed), B: 10mg (Fed) / Placebo (Fed) / 100mg (Fed), C: Placebo (Fed) / 50mg (Fed) / 100mg (Fed), D: 50mg (Fed) / 50mg (Fasted) , E: 50mg (Fasted) / 50mg (Fed)

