10.9.6. Pharmacokinetic Tables

Pharmacokinetic: Tables					
No.	Population	IDSL / TST ID / Example Shell	Title	Programming Notes	Deliverable [Priority]
Part 1					
3.1.	PK	PK01: pkct1	Summary of GSK1325756 Blood Concentration (ng/mL) (Part 1)		PR [1]
3.2.	PK	PK03: pkpt1	Summary of GSK1325756 Pharmacokinetic Parameters (non-transformed) (Part 1)		PR [1]
3.3.	PK	PK05: pkpt3	Summary of GSK1325756 Pharmacokinetic Parameters (loge-transformed) (Part 1)		PR [1]
3.4.	PK	Study Specific (PK_T1)	Analysis of Power Model Analysis for GSK1325756 Dose Proportionality of Pharmacokinetic Parameters (AUC(0-t), Cmax) (Part 1)	Parameter, Effect, n, Point estimate of Slope, SE, 90% CI	PR [1]
Part 2					
3.5.	PK	PK01: pkct1	Summary of GSK1325756 Blood Concentration (ng/mL) (Part 2)		SAC [2]
3.6.	PK	PK03: pkpt1	Summary of GSK1325756 Pharmacokinetic Parameters (non-transformed) (Part 2)		SAC [2]
3.7.	PK	PK05: pkpt3	Summary of GSK1325756 Pharmacokinetic Parameters (loge-transformed) (Part 2)		SAC [2]
3.8.	PK	Study Specific (PK_T2)	Analysis of food effect for Pharmacokinetic Parameters (AUC(0-t), Cmax) (Part 2)	n, Geometric mean of Fasted and Fed, ratio (Fasted/Fed), 90% CI and CVw(%)	SAC [2]

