			14	21	xxxx.xx	(xxxx.xx, xxxx.xx)	xx.xxx	xx.xx
	50mg	24	1	24	xxxx.xx	(xxxx.xx, xxxx.xx)	xx.xxx	xx.xx
			14	24	xxxx.xx	(xxxx.xx, xxxx.xx)	xx.xxx	xx.xx
	100mg	24	1	24	xxxx.xx	(xxxx.xx, xxxx.xx)	xx.xxx	xx.xx
			14	23	xxxx.xx	(xxxx.xx, xxxx.xx)	xx.xxx	xx.xx
	200mg	24	1	24	xxxx.xx	(xxxx.xx, xxxx.xx)	xx.xxx	xx.xx
			14	21	xxxx.xx	(xxxx.xx, xxxx.xx)	xx.xxx	xx.xx

USER ID: directory/program.sas DDMMYYYY hh:mm

CONFIDENTIAL

206817

Example: PK_T1
Protocol: GSK123456
Population: xxxxx

Page 1 of n

Table x.x

xxxxxxxxxxxxxxxxxxxxxxxxxxxxxx

Parameter	Effect	n	Slope	Point	SE	90% CI
			Estimate			
Parameter1	Log (dose levels)	xx	xxx	xxx	xxx	(xx, xx)
Parameter2	Log (dose levels)	xx	xxx	xxx	xxx	(xx, xx)
.
.
.

USER ID: directory/program.sas DDMMYY YYYY hh:mm

CONFIDENTIAL

206817

Example: PK_T2
Protocol: GSK123456
Population: xxxxx

Page 1 of n

Table x.x

xxxxxxxxxxxxxxxxxxxxxxxxxxxxxx

Parameter	Treatment	N	n	Geometric LS Mean	Ratio (Fasted/Fed)	90% CI	CVw(%) [1]
Parameter1 (unit)	Trt1	xx	xx	xxx	xxx	(xx, xx)	xx
	Trt2	xx	xx	xxx			
Parameter2 (unit)	Trt1	xx	xx	xxx	xxx	(xx, xx)	xx
.
.
.
ParameterX (unit)	xx	xx	xx	xxx	xxx	(xx, xx)	xx

[figure not shown]
USER ID: directory/program.sas DDMMYYYY hh:mm

Example: PK16b
Protocol: GSK123456
Population: xxxxx

Page 1 of n

Figure x.x

xxxxxxxxxxxxxxxxxxxxxxxxxxxx

USER ID: directory/program.sas DDMMYY YYYY hh:mm

[figure not shown]
[figure not shown]
Example: PK24
Protocol: GSK123456
Population: xxxxx

Page 1 of n

Figure x.x

xxxxxxxxxxxxxxxxxxxxxxxxxxxxxx

Treatment = tablet original fed

[figure not shown]
USER ID: directory/program.sas DDMMYYYY hh:mm

Example: PK18
Protocol: GSK123456
Population: xxxxx

Page 1 of n

Figure x.x

xxxxxxxxxxxxxxxxxxxxxxxxxxxx

[figure not shown]
USER ID: directory/program.sas DDMMYYYY hh:mm

Example: PK_F1
Protocol: GSK123456
Population: xxxxx

Page 1 of n

Figure x.x

xxxxxxxxxxxxxxxxxxxxxxxxxxxx

[figure not shown]
USER ID: directory/program.sas DDMMYYYY hh:mm

Example: PK28
Protocol: GSK123456
Population: xxxxx

Page 1 of n

Figure x.x

xxxxxxxxxxxxxxxxxxxxxxxxxxxx

USER ID: directory/program.sas DDMMYYYY hh:mm

CONFIDENTIAL

206817

Example: PK08 (pkcl1x)

Protocol: GSK123456

Population: xxxxx

Page 1 of n

Listing x.x

xxxxxxxxxxxxxxxxxxxxxxxxxxxxxx

{ Inv. / } Subj.	{ Age (y) / Sex/ Race }	Period /Tmt.	Date	Study		Actual Time dev. (units)	Actual Relative Time	Concentration (units)		
				Day / Period	Planned Relative Time					

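### Part 1 power model: the SAP adds period as a fixed effect, but each active dose is given in one period only, so with categorical period the dose-proportionality slope cannot be estimated

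*SAP*

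**What the plan says.** SAP 8.3.3.1 first displays a power model with an intercept, a random subject effect, a slope on log-dose and a residual. Dose is indexed over 10, 50 and 100 mg, and there is no period term. The text below the equation then says: "A mixed effect model will be fitted with the loge transformed dose and period as fixed effects". The sentence stands in both the SAP and its Amendment 1. It does not say whether period is a factor or a number.

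Protocol 10.3.2 gives the same equation without period and says: "Following loge-transformation, AUC(0-t) and Cmax will be separately analyzed using a power model with fixed effect terms for log-dose, as data permitted". SAP 2.1 states: "There were no changes or deviations to the originally planned statistical analysis specified in the protocol".

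For Part 2, SAP 8.3.3.2 writes a period effect into the equation, indexed by level, and the text matches it: "separately analysed using a mixed effects model fitting terms for treatment and period as fixed effects".

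The Part 1 result goes to Table 3.4, whose programming note in SAP 10.9.6 reads: "Parameter, Effect, n, Point estimate of Slope, SE, 90% CI".

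**The concern.** Part 1 is an ascending-dose design in which every sequence moves through the doses in the same order. Dose level and period therefore coincide among the active-dose records. A model with both log-dose and a period factor asks the data to separate two things that the design never varies independently.

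Table 3.4 is the only model-based dose-proportionality result in the plan. If the analysis is programmed as the sentence reads, its key number either cannot be produced or is an artefact of how the software resolves a singular model. The same data could then read as less than or more than dose-proportional, depending on a coding choice that nobody prespecified.

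**Working it through.** **Inputs**
- Sequences by period (protocol Table 2 and SAP 10.4.2): A is 10 mg / 50 mg / placebo. The other two are listed in the SAP footnote ("B: 10mg (Fed) / Placebo (Fed) / 100mg (Fed), C: Placebo (Fed) / 50mg (Fed) / 100mg (Fed").
- Six subjects per sequence, 18 in total (protocol 5.1). Each has two active periods, giving 36 records, 12 per dose.
- Between-subject CV 30.2% for AUC(0-t) (protocol 10.1.1, Part 1).
- Within-subject CV (CVw) for Part 1: not given. I assume 10% to 44.7%; the upper end is the Part 2 planning figure in protocol 10.1.1.

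**The plan's own Part 1 figure.** The protocol states no precision for the slope, only for a mean at n = 12: exp(t(0.95, 11) × √(ln(1 + CV²)/12)) − 1. This gives 16.55%, 18.25% and 19.95% at CV 30.2%, 33.2% and 36.2%. The protocol's 16.6%, 18.3% and 20.0% are reproduced, so the design inputs are read correctly.

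**Step 1: dose against period, active records**

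| Period | Sequences on active drug | Dose |
|---|---|---|
| 1 | A, B | 10 mg only |
| 2 | A, C | 50 mg only |
| 3 | B, C | 100 mg only |

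Placebo periods do not help: placebo has no log-dose and is not a dose level in the model. Replacements do not help either, because protocol 5.2 says "additional subjects may be enrolled as replacement subjects and assigned to the same treatment sequence, if applicable".

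**Step 2: estimability with categorical period**
- Rank of [intercept, period] = 3; rank of [intercept, log-dose, period] = 3.
- With subject columns: 20 and 20.

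Log-dose adds nothing to the column space, so the slope is not estimable. This is algebra and needs no variance assumption. A random subject effect and Kenward-Roger degrees of freedom do not change it.

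**Step 3: what software might print.** Put log-dose first and let the program drop aliased period columns. Centred log-doses are −1.304, 0.305 and 0.999, with sum of squares 2.791. Each subject's two doses are balanced across sequences, so the slope SE relative to the log-dose-only model is √(2.791 / remaining sum of squares).
- Last period as reference: a Period 1 column is kept and the slope is a 50-versus-100 mg contrast. Remaining (ln 2)²/2 = 0.240; ratio √(2.791/0.240) = 3.41. The weights on the 10 mg records sum to zero, so those records act only as subject adjustment.
- First period as reference: a Period 2 column is kept and the slope is a 10-versus-100 mg contrast. Remaining (ln 10)²/2 = 2.651; ratio √(2.791/2.651) = 1.03.
- Period as a linear number (written nowhere in the SAP): remaining 2.791 − 2.651 = 0.140; ratio √(2.791/0.140) = 4.47. Correlation of log-dose with period is 0.975 and the variance inflation factor is 19.9. The slope then rests only on curvature across the three dose means.

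**Step 4: 90% CI half-widths for the slope.** Between-subject CV is 30.2%. Half-width = t(0.95, df) × SE, with 17 df without period (t = 1.740) and 16 df with one period column (t = 1.746).

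| Assumed CVw | SE, log-dose only | Log-dose only | First-period ref. | Last-period ref. | Linear period |
|---|---|---|---|---|---|
| 10% | 0.0197 | 0.03 | 0.04 | 0.12 | 0.15 |
| 20% | 0.0384 | 0.07 | 0.07 | 0.23 | 0.30 |
| 44.7% | 0.0787 | 0.14 | 0.14 | 0.47 | 0.61 |

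**Step 5: effect on the estimate.** Assume geometric-mean ratios of 5.0 (50 vs 10 mg) and 1.6 (100 vs 50 mg), so log means are 0, ln 5 and ln 8.
- Log-dose only: (0.305 × ln 5 + 0.999 × ln 8) / 2.791 = 0.92.
- Last-period reference: ln 1.6 / ln 2 = 0.68.
- First-period reference: ln 8 / ln 10 = 0.90.
- Linear period: (ln 5 − ln 1.6) / (ln 5 − ln 2) = 1.24.

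**The case against.** The strongest reply is that little hangs on this. The model is exploratory, no hypothesis is tested and no acceptance range is set. Escalation and the start of Part 2 rest on safety and concentration review. The estimable model is already written in the protocol and in the SAP's own equation, and a statistician would probably notice the singular fit and follow the equation. All of that is true. It limits the harm but does not make the sentence executable, and a prespecified analysis should not depend on someone overriding its text.

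Three narrower points also stand:
- The Table 3.4 shell in SAP 10.10.3 shows a single effect ("Log (dose levels"), but this is weak evidence against period. The Part 2 shell shows no period effect either, although period is in that model.
- Under a first-period reference the SE rises only about 3%, and in the example the slope moves only from 0.92 to 0.90. The damage is arbitrariness, not uniformly large inflation.
- Protocol 10.3 leaves full analysis details to the analysis plan, so adding a term is not forbidden. SAP 2.1 nevertheless declares no change.

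The SAP's proviso that the models are fitted if the data allow does not help. The aliasing comes from the design and is present with complete data.

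**Conclusion.** The concern holds. With period as a categorical factor, the only coding the SAP uses for period in a model equation, the Part 1 slope is not estimable: rank 3 with and without log-dose. That result rests only on the sequence table and the three doses in the model.

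The size of the consequence is conditional. Depending on the constraint, the SE is about 1.03 or 3.4 times that of the log-dose-only model; a linear period term makes it about 4.5 times. These ratios do not depend on the variances. The half-widths do depend on an assumed Part 1 CVw, and the example slopes on assumed geometric-mean ratios.

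The sentence also conflicts with the equation above it and with the protocol model, although SAP 2.1 declares no change. The descriptive PK summaries, dose plots, safety displays and Part 2 food-effect model are unaffected.

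**What to change.** In SAP 8.3.3.1, delete the words adding period, so that log-dose is the only fixed effect, with subject random and Kenward-Roger degrees of freedom. This agrees with protocol 10.3.2 and the SAP's displayed equation, and it brings the power model back into line with SAP 2.1.

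Add one sentence: *Dose is confounded with period by the ascending design, so the slope is interpreted assuming no period effect.* Deleting the term makes the slope estimable, but it does not remove that confounding, and readers of Table 3.4 should be told so.

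The cost is one deletion and one added sentence in the SAP. No data collection, sample size or participant procedure changes.
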